Study Design	
This is a Phase 2, prospective, randomized, blinded, sham procedure-controlled, multicenter trial to assess the efficacy and safety of renal denervation by alcohol-mediated neurolysis using the Peregrine Kit. Subjects with a documented history of uncontrolled hypertension who are taking 0, 1, or 2 antihypertensive medications at enrollment will be recruited. Following screening, eligible subjects will enter a 4-week run-in period during which they will take no antihypertensive medications.
 
Subjects who continue to be eligible at the end of the run-in period will attend the study site for the day of procedure. All subjects will receive sedation and analgesia and undergo a diagnostic renal angiogram per standard procedures. Note: the type of sedation and analgesia will take into account the subject's preference, the interventionalist's and anesthesiologist's standard of practice, and institutional policy for this type of procedure. Subjects will then be randomized in a 1:1 ratio to one of the following 2 groups via central randomization (stratified by study site):
 
 • Treatment Arm: renal denervation (using the Peregrine Kit) performed with alcohol (0.6 mL per treated renal artery) infused through the Peregrine Catheter (minimum treatment: the 2 main renal arteries [1 per side]; physician is also permitted to treat up to 1 additional accessory artery on each side. Thus, the planned maximum total dose is 4 x 0.6 mL = 2.4 mL.) • Sham Control Arm: only renal angiography performed. No renal denervation and no alcohol infusion will be performed. 
Subjects will be discharged from the study site the day after the procedure if there are no safety concerns, per the physician's judgment. Subjects with an estimated glomerular filtration rate (eGFR) of >45 and <60 mL/min/1.73 m² will return to provide a blood sample for measurement of serum creatinine 48 to 96 hours after the procedure. Subjects will continue to take no antihypertensive medications during the first 8 weeks after the procedure (except for emergencies, as defined

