If ANY of the following exclusion criteria are met, the subject must be excluded from the trial and cannot be randomized or undergo the procedure:

1. Subject has a contraindication known for conventional percutaneous interventional procedures such as:
 - Intolerance for antiplatelet/anticoagulant therapy
 - Known allergy to contrast media that cannot be adequately pre-medicated
 - Bleeding/coagulation disorders (such as bleeding diathesis, thrombocytopenia, and severe anemia)
 - Occlusive peripheral vascular disease that would preclude percutaneous femoral access for the procedure.

2. Subject has an acute or sub-acute infection that the investigator judges would pose unacceptable procedural risks to the subject.
3. Subject has imaging-assessed renal artery anatomy abnormalities or variations based on investigator's evaluation of the screening images (i.e. magnetic resonance angiography [MRA]/computed tomography angiography [CTA] examination and/or renal angiography) meeting one of the following criteria:
 - Main renal artery that has a diameter of <4 mm or >7 mm and length of <5 mm
 - Accessory renal arteries with diameter >2 mm or <4 mm, which supply >20% of the whole kidney parenchyma on that side, per the investigator's judgment. NOTE: subjects with more than one eligible accessory renal artery per side will be excluded.
 - Renal artery stenosis >50% of the normal diameter segment (diameter stenosis, compared to the angiographically normal proximal or distal segment)
 - Any renal artery abnormality or disease that, per the physician assessment, precludes the safe insertion of the guiding catheter (including, but not limited to, severe renal artery aneurysm, excessive tortuosity, severe renal artery calcification)
 - Previous renal angioplasty associated with stenting or other implants, that, per the physician's assessment, precludes the safe deployment of the Peregrine Catheter components in the target treatment segment of the renal artery
 - Previous renal denervation
 - Fibromuscular dysplasia of the renal arteries.
4. Subject has documented severe untreated obstructive sleep apnea (apnea hypopnea index [AHI] ≥30 per hour).
5. Subject has documented diagnosis of the following causes of hypertension: Cushing's disease or Cushing's Syndrome, hyperaldosteronism, pheochromocytoma, thyroid and parathyroid abnormalities, or onset of hypertension prior to the age of 18.
6. Subject has a history of pre-eclampsia.

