4. PATIENT POPULATIONS

4.1. Data Sets to be Analyzed

The Intent-to-Treat (ITT) Analysis Set will include all subjects who were randomized regardless of whether treatment was received. Subjects will be analyzed according to their randomized treatment group, irrespective of treatment received.

The Safety Analysis Set will include all subjects who received treatment. Subjects will be analyzed according to the actual treatment received, irrespective of treatment assignment.

The Per-Protocol (PP) Analysis Set will include subjects with no important protocol deviations. Subjects will be analyzed according to the actual treatment received. Important protocol deviations include:

- Not meeting inclusion/exclusion criteria
- Not receiving bi-lateral treatment or an unsuccessful procedure
- Receiving anti-hypertensive treatment prior to evaluation of the primary ambulatory blood pressure monitoring (ABPM) measurement
- Not completing the primary ABPM measurement

All deviations will be reviewed prior to unblinding to assess if additional exclusions will be applied.

Unless otherwise noted, the ITT and PP Analysis Sets will be used for all efficacy analyses and safety analyses will be conducted in the Safety Analysis Set.

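### Exclusion Criterion 3: every diameter meets the accessory-artery limit, and under either literal reading the main-artery line leaves in vessels that breach one of its stated figures

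*Protocol*

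**What the plan says.** The Exclusion Criteria in the Protocol Synopsis are absolute: "If ANY of the following exclusion criteria are met, the subject must be excluded from the trial". Criterion 3 covers renal anatomy and applies to a subject "meeting one of the following criteria", so each bullet under it must work on its own.

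- Main artery: "Main renal artery that has a diameter of <4 mm or >7 mm and length of <5 mm".
- Accessory artery: "Accessory renal arteries with diameter >2 mm or <4 mm, which supply >20% of the whole kidney parenchyma on that side", as assessed by the investigator. A note in the same bullet adds that "subjects with more than one eligible accessory renal artery per side will be excluded".

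The Study Design part of the synopsis, and SAP Section 3.2, describe the Treatment Arm as treating at least the two main arteries. They add that the "physician is also permitted to treat up to 1 additional accessory artery on each side", which gives the maximum of 4 x 0.6 mL = 2.4 mL.

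SAP Section 4.1 counts "Not meeting inclusion/exclusion criteria" among the important deviations that remove a subject from the Per-Protocol set. SAP Section 5.4 makes that set supportive for the primary endpoint.

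**The concern.** An exclusion rule has to sort subjects the same way wherever it is read. In the accessory bullet, the two diameter limits are joined by a word that makes the condition true for every vessel. In the main-artery bullet, a joint condition on width and length appears where separate limits may have been meant.

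Two things are at stake. The first is which anatomies enter a trial of an endovascular device. About 90 subjects over about 25 sites is 90 / 25 = 3.6 per site, and each site's investigator evaluates the images, so local readings could differ. The second is the analysis. The same subject can be an eligibility violation under one reading and compliant under another, and so drop out of or stay in the Per-Protocol set.

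**Working it through.** The plan gives no figure to reproduce here; the check is one of logic. D is diameter and L is length, both in mm.

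**Accessory bullet.** As written, a subject is excluded if (D > 2 or D < 4) and the share of parenchyma is above 20%.

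1. To fail the diameter part, a vessel would need D ≤ 2 and D ≥ 4 together, which is impossible. For example, 1.5 mm passes on < 4, 4.5 mm passes on > 2, and 3.0 mm passes on both. All values from 0.5 to 10.0 mm in steps of 0.1 satisfy it.
2. The bullet therefore reduces to share > 20%, at any diameter. An accessory artery supplying 20% or less is not caught by it, at any diameter.
3. The intended limit cannot be recovered from the wording. With *and* in place of *or*, the diameter part holds only for 2 < D < 4 (2.1 to 3.9 on the same grid). A rule meant to catch vessels outside those figures would do the reverse. The two disagree on 1.5, 3.0 and 4.5 mm alike.

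**Main-artery bullet.** There are two literal groupings, and a third reading that treats the items as a list of alternatives:

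- A: (D < 4 or D > 7) and L < 5
- B: D < 4 or (D > 7 and L < 5)
- C: D < 4 or D > 7 or L < 5

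| D | L | A excludes | B excludes | C excludes |
|---|---|---|---|---|
| 3.5 | 4 | yes | yes | yes |
| 3.5 | 10 | no | yes | yes |
| 5.5 | 4 | no | no | yes |
| 5.5 | 10 | no | no | no |
| 7.5 | 4 | yes | yes | yes |
| 7.5 | 10 | no | no | yes |

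Two regions escape both A and B. If D > 7 and L ≥ 5, the length term fails in each and D < 4 is false. If 4 ≤ D ≤ 7, every diameter term is false whatever L is, so a vessel shorter than 5 mm stays in. A and B differ only where D < 4 and L ≥ 5.

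The other bullets of Criterion 3 (stenosis, abnormality that prevents safe guiding-catheter insertion, stents or implants, earlier denervation, fibromuscular dysplasia) restore no width or length limit.

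**Effect on the Per-Protocol set.** Take a treated subject with one accessory artery supplying more than 20%. Read literally, this is an eligibility breach and the subject leaves the set. Under a rule that accepts that artery, the subject stays, other deviations aside. Each such subject is 1 of about 45 in an arm: 1 / 45 = 2.2%.

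**The case against.** Several points on the other side have weight.

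- *The accessory bullet need not contradict the design.* A reader might infer that the criterion excludes the very subjects the design plans to treat. The documents do not support that. Arteries supplying 20% or less escape the bullet and can be both the eligible arteries of the note and the one per side that may be treated. Neither the Study Design text nor SAP Section 3.2 sets a parenchyma share. What stands is narrower: the relation is unclear for arteries above 20%.
- *The main-artery line has more than one parsing.* A reader might infer that a 3 mm wide, 20 mm long artery passes as written. It does under A but not under B, so that example should not be relied on. Reading C removes the defect, and the protocol does use *and* between alternatives in Exclusion Criterion 15, but there the words *any of* make it explicit. Inclusion Criteria 3 and 8 use AND for a true joint requirement. C is possible, not established.
- *The protocol body is not in the available text*, which holds the synopsis, schedules, figure notes and Appendix I. The body may define the term or state the limits differently. The point is therefore confined to the synopsis.
- *Timing.* This protocol version is dated 14 DEC 2021 and primary endpoint completion was planned for JUN 2021. On those dates, new wording would not change who is randomized in the main study.
- *Physician assessment* of catheter safety gives some protection. It does not replace numeric limits.

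**Conclusion.** The point holds for the synopsis wording. The accessory diameter limit discriminates nothing, because every diameter satisfies it. The main-artery line leaves two groups unexcluded under both literal groupings: wider than 7 mm with length at least 5 mm, and 4 to 7 mm wide with length below 5 mm. The status of widths below 4 mm with adequate length is ambiguous. Followed literally, the rule gives results at odds with its own figures. It should be corrected, since it bears on safety and on Per-Protocol membership.

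Two further inferences are not supported. One is that the 2.4 mL maximum can hardly be reached: two accessory arteries at or below 20%, one per side, would reach it, and the documents give no distribution of accessory-artery size or supply. The other is that the primary comparison is biased: randomization follows diagnostic angiography, and the criterion applies to both arms alike.

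On the planned dates, the practical effect is mainly on deviation and Per-Protocol classification, and on the crossover phase if its criteria reuse the wording. The number of subjects concerned is unknown. Two assumptions remain: that the protocol body does not already settle the matter, and that the version in force at screening carried the same wording. SAP Section 2 cites Version 6.0, which is not available here.

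**What to change.** 1. Reconcile Criterion 3 with its note, with the Study Design text and with SAP Section 3.2. Define the eligible accessory renal artery.
2. State each diameter and length condition as its own testable line, with the connectives explicit. The sponsor must decide the intended limits; none is proposed here.
3. Check whether the crossover eligibility criteria, which Table 2 footnote 4 refers to but the available text does not show, carry the same wording.
4. From imaging on file, list every randomized subject whose eligibility differs between the literal and the reconciled rule. Use that list in the deviation review that SAP Section 4.1 places before unblinding, so that important deviations and the Per-Protocol set are classified under one documented rule.

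The cost is a wording change or clarification letter and a check of existing screening images. No new data are needed, and the primary Intent-to-Treat analysis is unchanged.

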Appendix I Proposed Structured Drug Titration

After 8 weeks post-treatment, subjects may take antihypertensive medications to maintain a target office SBP of <140 mmHg and ≥ 90 mmHg (based on a mean of 3 measurements). The titration regimen provided in the following table should be followed if possible.

Step (Target SBP <140 mmHg and ≥ 90 mmHg) ¹	Drug	Treatment Score
0 (not needed)	None	0
1 (if needed)	CCB: mid-dose	1
2 (if needed)	ACE inhibitor or ARB: full dose	2
3 (if needed)	Hydrochlorothiazide 12.5 mg	3
4 (if needed)	Hydrochlorothiazide 25 mg	4
5 (if needed)	CCB: increase to full dose	5
6 (if needed)	Spironolactone or beta-blocker or clonidine	6
7 (if needed)	Spironolactone or beta-blocker or clonidine	7
8 (if needed)	Spironolactone or beta-blocker or clonidine	8

Abbreviations: ACE = angiotensin-converting enzyme; ARB = angiotensin receptor blocker; BP = blood pressure; CCB = calcium channel blocker; SBP = systolic blood pressure.

1 There will usually be 2 to 3 weeks between steps. If the target is reached, there are no further steps even if BP fluctuates above the target. For Steps 6, 7, and 8, the choice of drug and dose is at the investigator's discretion. If initial systolic BP is ≥ 160 mmHg, Steps 1 and 2 can be combined. Fixed-combination drug products can be used to decrease pill burden.

Source: Weber MA, Kirtane A, Mauri L, et al. Renal denervation for the treatment of hypertension: making a new start, getting it right. *J Clin Hypertens* 2015;17(10):743-50.

1. LIST OF ABBREVIATIONS AND DEFINITIONS OF TERMS

ABP ambulatory blood pressure

ABPM ambulatory blood pressure monitoring

AE adverse event

ANCOVA analysis of covariance ASI Ablative Solutions, Inc.

BP blood pressure

COVID-19 coronavirus disease of 2019

CRF Case Report Form

CTA computed tomography angiography

CVA cerebrovascular accident

DSMB Data Safety Monitoring Board

DDD defined daily dose
DUS duplex ultrasound
ECG electrocardiogram
EF ejection fraction

eGFR estimated glomerular filtration rate

ITT Intent-to-Treat
MAE major adverse event

MedDRA Medical Dictionary for Regulatory Activities

MI myocardial infarction

MRA magnetic resonance angiography NYHA New York Heart Association

PP Per Protocol PT Preferred Term

SAP statistical analysis plan SAE serious adverse event SOC System Organ Class

TEAE treatment emergent adverse event UADE unanticipated adverse device effect

WHO World Health Organization

2. INTRODUCTION

This statistical analysis plan (SAP) in conjunction with the table shells is intended to prospectively (a priori) outline the analyses and presentations of data that will form the basis for conclusions to be reached to answer the study objectives outlined in the protocol, and to explain in detail how the data will be handled and analyzed, adhering to commonly accepted standards and practices of biostatistical analysis in clinical trials. Results obtained from the analyses outlined in this document will be the basis of the Clinical Study Report for this study. This plan is based on Version 6.0 of the study protocol dated 01 July 2020.

3. INVESTIGATIONAL PLAN

3.1. Study Objective

The primary objective of this proof-of-concept study is to evaluate the efficacy of renal denervation by alcohol-mediated neurolysis using the Peregrine SystemTM Kit (also referred to as Peregrine Kit) in hypertensive subjects, when used in the absence of antihypertensive medications, as evaluated by change in mean 24-hour ambulatory systolic blood pressure (SBP) from baseline to 8 weeks post-treatment.

Secondary objectives are to evaluate the acute and chronic safety of renal denervation by alcohol-mediated neurolysis using the Peregrine Kit in hypertensive subjects, up to 2 years post-treatment and to evaluate the efficacy of renal denervation by alcohol-mediated neurolysis using the Peregrine Kit on blood pressure in hypertensive subjects, up to 1 year post-treatment.

3.2. Overall Study Design and Plan

This is a Phase 2, prospective, randomized, blinded, sham procedure-controlled, multicenter trial to assess the efficacy and safety of renal denervation by alcohol-mediated neurolysis using the Peregrine Kit. Subjects with a documented history of uncontrolled hypertension who are taking 0, 1, or 2 antihypertensive medications at enrollment will be recruited. Following screening, eligible subjects will enter a 4-week run in period during which they will take no antihypertensive medications.

Subjects who continue to be eligible at the end of the run-in period will be randomized in a 1:1 ratio to one of the following 2 groups via central randomization (stratified by study site):

- Treatment Arm: renal denervation (using the Peregrine Kit) performed with alcohol (0.6 mL per treated renal artery) infused through the Peregrine Catheter (minimum treatment: the 2 main renal arteries [1 per side]; physician is also permitted to treat up to 1 additional accessory artery on each side. Thus, the planned maximum total dose of alcohol is 4 x 0.6 mL = 2.4 mL.)
- Sham Control Arm: only renal angiography will be performed. No renal denervation and no alcohol infusion will be performed.

Subjects will be discharged from the study site the day after the procedure if there are no safety concerns, per the physician's judgment. Subjects with an estimated glomerular filtration rate (eGFR) of >45 and <60 mL/min/1.73 m² will return to provide a blood sample for measurement of serum creatinine 48 to 96 hours after the procedure. Subjects will continue to take no antihypertensive medications during the first 8 weeks after the procedure (except for emergencies, as defined in the protocol). After 8 weeks, antihypertensive medications are permitted according to the protocol-defined criteria and proposed titration scheme.

Follow-up visits will be performed at 4 weeks, 8 weeks, 3 months, 6 months, 1 year, and 2 years, as well as telephone contacts at 2 and 6 weeks in Ireland only.

The study will be unblinded after the last subject has completed the 6-month visit.

Crossover from the Sham Control Arm to the Treatment Arm may be allowed, at the discretion of the treating investigator, after the Data Safety Monitoring Board (DSMB) has reviewed the 6-month data from all subjects, the study has been unblinded, and the subject has completed the 1-year follow-up visit.

A subject is considered enrolled once he/she signs the informed consent form. All enrolled subjects will then proceed to complete the screening and baseline tests. If they do not meet the study criteria, they will be withdrawn from the study (status Screen Failure) and will not count towards the treated study population.

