	
in the protocol). After 8 weeks, antihypertensive medications are permitted according to the protocol-defined criteria and proposed titration scheme.
 
Follow-up visits will be performed at 4 weeks, 8 weeks, 3 months, 6 months, 1 year, and 2 years.
 
The study will be unblinded after the last subject has completed the 1-year follow-up visit.
 
Crossover from the Sham Control Arm to the Treatment Arm may be allowed, at the discretion of the treating investigator, after the Data Safety Monitoring Board (DSMB) has reviewed the 1-year data from all subjects and the study has been unblinded.

Study Geography/ Number of Planned Investigational Sites	United States (US) and Europe Multicenter trial with approximately 25 investigational sites (in the US and Europe)
Number of Groups/ Arms/Cohorts	2 groups (Treatment Arm, Sham Control Arm; randomized 1:1)
Number of Targeted Subject Treatment, Total and in Each Arm	Approximately 90 subjects randomized: 
 • 45 subjects in the Treatment Arm • 45 subjects in the Sham Control Arm
Planned Duration of Subject Participation	Approximately 26 months* (for each subject) 
 • Screening period: approximately 4 to 8 weeks • Run-in period: 4 weeks • In-hospital period: 2 days • Follow-up period: 2 years 
*May be different for subjects in Sham Control Arm in the case of crossover: subjects will have a final 1-year follow-up visit after crossover treatment.

INVESTIGATIONAL PRODUCT(S), DOSE AND MODE OF ADMINISTRATION	
Active Product	
Combination Product: Peregrine System Kit
 
Drug Constituent Part: Dehydrated Alcohol Injection, USP
 
Device Constituent Part: Peregrine System Infusion Catheter
 
Dose: 0.6 mL alcohol per treated renal artery. Maximum total dose per subject = 2.4 mL at one treatment session (i.e. during the same procedure).
 
Dosage form: Solution for injection
 
Dosage frequency: Once during the study procedure
 
Mode of administration: Direct infusion to the perivascular space, during an endovascular procedure using the device constituent part

Placebo/Control/ Comparator	
In the Sham Control Arm, only renal angiography will be performed. No alcohol infusion (i.e. no renal denervation) will be performed.
 
Dosage form: Not applicable
 
Dosage frequency: Once during the study procedure
 
Mode of administration: Endovascular

SUBJECT SELECTION

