Changes from baseline will be computed as the paired mean difference and will be summarized with descriptive statistics (n, mean, SD, range, median). The 95% confidence interval (CI) of the difference between treatment groups at each time point will be computed. Categorical data will be summarized as frequencies and percentages. Relative risks and 95% CIs will be computed. Secondary efficacy endpoints are considered supportive and thus there is no adjustment to alpha for multiplicity with a single primary efficacy endpoint. Analysis of efficacy endpoints will be conducted in the ITT and PP Analysis Sets. For the primary efficacy endpoint analysis, the main population is considered the ITT, and the PP is considered supportive.

For all continuous primary and secondary blood pressure endpoints, changes over time will be additionally explored in mixed effects repeated measures analyses, including the values at all time points.

It is planned to conduct an 8-week blinded interim analysis, a 6-month blinded interim analysis, and an unblinded 1-year interim analysis after all subjects have completed the 1-year follow-up visit and the study has been unblinded.

Secondary safety endpoints:

- Major adverse events (MAEs) through 30 days post-treatment, as adjudicated by the Clinical Events Committee (CEC). An MAE is defined as any of the following:

¹ Townsend RR, Mahfoud F, Kandzari DE, et al. Catheter-based renal denervation in patients with uncontrolled hypertension in the absence of antihypertensive medications (SPYRAL HTN-OFF MED): a randomised, sham-controlled, proof-of-concept trial. Lancet 2017;390(10108):2160-70.

- All-cause death
- End-stage renal disease (ESRD) (eGFR <15 mL/min/1.73 m² or need for renal replacement therapy)
- Significant embolic event resulting in end-organ damage or requiring intervention to prevent it
- Major vascular complications, including major renal artery dissection, renal artery aneurysm or pseudoaneurysm that required intervention or led to renal artery stenosis (>60% diameter stenosis)
- Major bleeding related to renal denervation within the renal arteries, or related to the Peregrine Catheter when in the body (per protocol bleeding definition)

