- 2 At a screening visit, after written informed consent has been provided, initial screening assessments will be made. Subjects will then attend for magnetic resonance angiography (MRA) to assess renal vasculature before the start of the run-in period. For sites that would prefer to use computed tomography angiography (CTA) instead, agreement may be reached with the sponsor on a case-by-case basis (depending upon local regulatory approvals and site capacity). Subjects must have an estimated glomerular filtration rate (eGFR) of >45 mL/min/1.73 m² confirmed before imaging at screening. Subjects who are currently taking antihypertensive medications will down-titrate their medications, if necessary, so that they are taking 0 antihypertensive medications at the start of the run-in period.
- 3 Subjects will take 0 antihypertensive medications from the start of the run-in period (Week -4). During the run-in period, a safety visit will take place approximately 2 weeks before the procedure (Week -2). Further study assessments and a final check of eligibility criteria will be performed approximately 1 week before the procedure (Week -1), including office blood pressure and ambulatory blood pressure monitoring (ABPM) measurements.
- 4 Subjects may be admitted on Day -1 for logistical reasons. For the day of the procedure (Day 0), flexibility in scheduling is permitted (up to 1 week), e.g. due to cath lab availability, based on physician discretion and with careful consideration of subject safety. Randomization 1:1 (Treatment Arm : Sham Control Arm) will be performed in the cath lab/special procedure lab on the day of the procedure (Day 0), after the subject has been sedated and undergone diagnostic renal angiography.
- 5 Subjects will continue to use 0 antihypertensive medications during the first 8 weeks after the procedure (except for emergencies). After 8 weeks, antihypertensive medications are permitted, if necessary (see Appendix I).
- 6 Study unblinding will be performed after the last subject has completed the 1-year follow-up visit.
- 7 Crossover from the Sham Control Arm to the Treatment Arm may be allowed, at the discretion of the treating investigator, after the Data Safety Monitoring Board (DSMB) has reviewed the 1-year data from all subjects and the study has been unblinded.

Figure 2 Study Flow Diagram: Subject Screening, Run-in, and Treatment

BP = blood pressure; DBP = diastolic blood pressure; N = number of subjects; SBP = systolic blood pressure

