5.2.4. Interim Analyses and Data Monitoring

There are 2 planned interim analyses: a blinded 8-week interim analysis (conducted after all subjects have completed the 8-week visit), and an unblinded 6-month interim analysis (conducted after all subjects have completed the 6-month visit and the study has been unblinded).

Neither of the planned interim analyses for this study is intended to be assessed with the purpose of altering the study design or sample size.

The 8-week interim analysis will include available data through the 8-week assessment including, but not limited to, primary efficacy and safety data. The individual treatment assignments will remain blinded at this time. The 8-week interim analysis will be assessed by the unblinded DSMB in accordance with the DSMB charter. Analysis will be conducted by the independent unblinded DSMB statistician. Only aggregate data, by treatment group, will be provided outside of the DSMB. Data will be cleaned to the extent possible but not locked for this analysis. All outstanding adjudications for events occurring with 8-weeks should be resolved. A separate interim analysis plan will provide additional details as to the content and dissemination of these results.

The 6-month interim analysis will include all available data through 6 months. The study will be unblinded for analysis at this time. The 6-month interim analysis results will help inform the appropriateness of the crossover.

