6. CHANGES TO ANALYSES PLANNED IN THE PROTOCOL

There are no changes to the planned analyses in the protocol.

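### The supplied SAP, written to protocol v6.0, unblinds after the last 6-month visit with two interim analyses; protocol v7.0 unblinds after the last 1-year visit with three

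*SAP*

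**What the plan says.** **SAP.** Section 2 gives the basis: "This plan is based on Version 6.0 of the study protocol dated 01 July 2020". The last entry in the Section 7 change log is version 4.0, 19 November 2021. Section 3.2 says: "The study will be unblinded after the last subject has completed the 6-month visit". Section 5.2.4 plans two interim analyses, a blinded one at 8 weeks and an unblinded one at 6 months, and says of the second: "The study will be unblinded for analysis at this time". Section 6 says: "There are no changes to the planned analyses in the protocol".

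**Protocol.** The version supplied is 7.0, 14 December 2021. The synopsis (Study Design) says: "The study will be unblinded after the last subject has completed the 1-year follow-up visit". The notes to Figure 1 repeat it: "Study unblinding will be performed after the last subject has completed the 1-year follow-up visit". The statistical part of the synopsis plans "an 8-week blinded interim analysis, a 6-month blinded interim analysis, and an unblinded 1-year interim analysis".

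**Crossover.** SAP 3.2 asks for DSMB review of all subjects' 6-month data, unblinding, and the subject's own 1-year visit. Protocol v7.0 (synopsis, Table 1 footnote 25, Figure 1 notes) asks for DSMB review of all subjects' 1-year data and unblinding.

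**Endpoint time points.** In the SAP, change in eGFR and eGFR decreases above 25% (3.4.3, 5.5.1.2, 5.5.1.3) and increases or decreases in antihypertensive medication (3.4.2, 5.5.2.5) stop at 6 months. The v7.0 synopsis takes all three to 1 year.

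**The concern.** The two documents give incompatible instructions for the same 6-month analysis: v7.0 keeps it blinded, while the SAP breaks the blind in order to run it. SAP 5.2.4 is an operating instruction, not just a recap of the design, and SAP Section 2 makes this plan the basis of the Clinical Study Report.

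At stake are the 1-year data of subjects randomised late. Efficacy up to 1 year is a secondary objective, and the last scheduled ambulatory recording is at 1 year. After week 8, medication follows a titration scheme that leaves some choices to the investigator (Protocol Appendix I), and investigators judge whether adverse events are related. Such data are open to influence once allocation is known. The 1-year blood pressures also enter the repeated-measures model in SAP 5.6.

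A smaller matter comes from the same version lag: an analysis programmed strictly from the SAP's endpoint sections would not produce the 1-year count of eGFR decreases above 25% that v7.0 names.

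**Working it through.** The documents give no figure for the gap, so there is none to reproduce. The check compares the texts and then does date arithmetic.

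**1. Versions.** Last logged SAP version: 19 November 2021. Protocol v7.0: 14 December 2021. Difference: 11 days left in November + 14 in December = 25 days.

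**2. Texts side by side.**

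| Item | SAP v4.0 | Protocol v7.0 | Conflict? |
|---|---|---|---|
| Unblinding | last 6-month visit (3.2, 5.2.4) | last 1-year visit (synopsis, Figure 1 notes) | yes |
| Interim analyses | 2: 8-week blinded, 6-month unblinded (5.2.4) | 3: 8-week blinded, 6-month blinded, 1-year unblinded (synopsis) | yes |
| DSMB review before crossover | 6-month data (3.2) | 1-year data (synopsis, Table 1, Figure 1 notes) | yes |
| Subject's own 1-year visit before crossover | required (3.2, 5.2.3) | met, because crossover follows the last subject's 1-year visit | no |
| eGFR change and decrease >25% | 8 weeks, 6 months | 8 weeks, 6 months, 1 year | yes |
| Medication increases/decreases | to 6 months | to 6 months and 1 year | yes |

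**3. Gap between the two triggers, last subject.** Inputs from SAP 5.2.8: 6-month visit at day 180 ± 28; 1-year visit at day 365 ± 56.

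- Nominal: 365 − 180 = 185 days
- Shortest: (365 − 56) − (180 + 28) = 309 − 208 = 101 days
- Longest: (365 + 56) − (180 − 28) = 421 − 152 = 269 days

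**4. Who is exposed.** When the last subject reaches day 180, a subject randomised d days before that subject is at day 180 + d. The 1-year visit is still ahead if 180 + d < 365, that is d < 185. At nominal timing, everyone randomised in the final 185 days of accrual could have the 1-year visit after the SAP's trigger. The documents give neither the accrual pattern nor the time from trigger to release of the code, so this cannot be turned into a number of subjects.

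**5. What 1-year output the SAP already plans.** Medication counts at 1 and 2 years (5.7); laboratory summaries by visit, with shift tables at 1 and 2 years (5.10); medication tables covering the period after 8 weeks (14.2.7-1 and -2); an eGFR table (14.3.7-1) and an eGFR figure (Figure 5). What is chiefly left out is the 1-year proportion with an eGFR decrease above 25%.

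**The case against.** **The SAP is older than v7.0.** It says openly that it follows v6.0, and it could not have matched a protocol issued 25 days later. A later SAP may exist. All of this stands. It explains the conflict but does not remove it, because the supplied texts cannot both be followed. A reader might infer that Section 6 was wrong when written. The documents do not support that: v6.0 was not supplied, and the statement was made against v6.0. It simply does not hold against v7.0.

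**Access to the code may be governed elsewhere.** SAP 3.2.1 refers to a Randomization and Blinding Plan, which was not supplied. Harm also requires the sponsor to follow the older SAP over the newer protocol. Both points stand, so the harm is conditional.

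**SAP 5.2.3 might be read as a further crossover conflict.** It is not one. It mentions only the participant's own 1-year visit, which v7.0's later crossover point satisfies. Only the DSMB-review clause in SAP 3.2 differs.

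**A reader might infer from the synopsis dates that the SAP's trigger had passed before v7.0 was issued.** The visit windows do not allow that conclusion. Take study completion on 31 March 2023 with the last 2-year visit 56 days early: 31 March 2023 − (730 − 56) days puts last randomisation at 26 May 2021. Adding 180 days gives 22 November 2021, and a further 28 days gives 20 December 2021, after 14 December. These are also planned months, not events.

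**A reader might infer that 1-year output is missing altogether.** It is not, as step 5 of the working shows. Nor does v7.0 name a treatment-score analysis or a between-group eGFR test, so neither can be called missing at 1 year.

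**Conclusion.** The supplied SAP conflicts with protocol v7.0 on four matters: when the study is unblinded, the number and blinding of the interim analyses, the data the DSMB reviews before crossover, and the last time point of the named eGFR and medication-change endpoints. The point should be fixed.

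For the last subject the SAP's trigger is nominally 185 days earlier than the protocol's, with a range of 101 to 269 days. That rests only on the visit days and windows in SAP 5.2.8, with no assumed accrual rate or delay in releasing the code.

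The risk is limited to supportive 1-year blood pressure, medication and safety data. It would be wrong to conclude that the primary result is threatened: all 8-week visits precede either trigger, and SAP 5.2.1 treats the confidence intervals as descriptive. It would also be wrong to conclude that the blind was in fact broken early, because the documents do not record whether or when unblinding occurred.

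**What to change.** Re-issue the SAP against protocol v7.0, unless a later version already does this.

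- **If unblinding has not occurred:** set SAP 3.2 and 5.2.4 to the protocol's unblinding point and its three interim analyses.
- **If it has occurred:** state when and to whom, reconcile both documents (a blinded 6-month interim cannot then simply be written in), and report 1-year data collected after unblinding as such.
- **Crossover:** reconcile the DSMB-review clause in SAP 3.2 with the protocol synopsis, Table 1 footnote 25 and the Figure 1 notes. SAP 5.2.3 needs no change on this account.
- **Endpoints:** add 1 year to SAP 3.4.3, 5.5.1.2 and 5.5.1.3 for eGFR, and to 3.4.2 and 5.5.2.5 for medication use.
- **Version statements:** cite v7.0 in Section 2 and list any remaining departures in Section 6.

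The cost is an SAP amendment, plus a protocol correction or a documented note if the blind has already been broken. No new data, visits or subjects are needed: 1-year eGFR is in Protocol Table 3, and antihypertensive medication is recorded through 2 years (Table 1 footnote 24).
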